5 POPULATION

5.1 Number of Subjects

Approximately 15 adult subjects with moderate or severe OUD are planned to be dosed with SUBLOCADE.

5.2 Inclusion Criteria

Subjects must meet all of the following criteria:

1. Signed the informed consent form (ICF) and have the ability to comply with the requirements and restrictions listed therein.
2. Age: ≥ 18 years at the time of signing the ICF.
3. Have documented history of moderate or severe OUD as defined by Diagnostic and Statistical Manual of Mental Disorders, 5th Edition (DSM-5).
4. Seeking buprenorphine-assisted treatment for OUD and is an appropriate candidate in the opinion of the Investigator or medically qualified sub-Investigator.
5. A female subject is eligible to participate if she is not pregnant (as confirmed by a negative urine human chorionic gonadotrophin test), is not lactating and, if of childbearing potential, agrees not to become pregnant while on the study and use medically acceptable means of contraception while on the study. The following methods of contraception are considered to be medically acceptable: established use of oral, injected or implanted hormonal contraception; placement of an intrauterine device or intrauterine system; use of a double-barrier method of contraception (condom or occlusive cap with use of a spermicide).

5.3 Exclusion Criteria

1. Current diagnosis, other than OUD, requiring chronic opioid treatment.
 2. Meet DSM-5 criteria for severe alcohol-use disorder.
 3. Has received any medication assisted treatment within 2 weeks.
 4. Concurrent or prior treatment with any long-acting depot form of buprenorphine-containing products.
 5. Concurrent treatment with another investigational agent or enrolment in another clinical study (except for an observational study) or treatment with another investigational agent within 30 days prior to screening.
-

6. Concurrent treatment with medications contraindicated for use with buprenorphine as per local prescribing information, including benzodiazepines or any other central nervous system depressants.
 7. Significant traumatic injury, major surgical procedure (as defined by the Investigator) within 30 days prior to Day 1 or still recovering from prior surgery.
 8. Any other active medical condition, organ disease or concurrent medication or treatment that may either compromise subject safety or interfere with study endpoints.
 9. Congenital long QT syndrome, history of prolonged QT in the 3 months prior to screening, or a corrected QT interval (Fridericia's – QTcF) >450 msec (male) or >470 msec (female), or history of risk factors for Torsades de Pointes. Known personal and/or family history of congenital QT prolongation, or taking Class IA antiarrhythmic medications (e.g., quinidine, procainamide, disopyramide) or Class III antiarrhythmic medications (e.g., sotalol, amiodarone) or other medications that prolong the QT interval. Known family history of sudden unexplained death.
 10. Total bilirubin $\geq 1.5 \times$ ULN, ALT $\geq 3 \times$ ULN, AST $\geq 5 \times$ ULN, serum creatinine $> 2 \times$ ULN at screening.
 11. Abdominal area unsuitable for SC injections (e.g., nodules, lesions, excessive pigment, infected, scarring).
 12. Uncontrolled intercurrent illness including, but not limited to, a medical or psychiatric illness/social situation that would limit compliance with study requirements or compromise the ability of the subject to provide written informed consent.
 13. Known allergy or hypersensitivity to buprenorphine, ATRIGEL or their excipients.
 14. Subject to court order requiring treatment for OUD.
 15. Subjects who are unable, in the opinion of the Investigator or Indivior, to comply fully with the study requirements including those who are currently incarcerated or pending incarceration/legal action.
 16. Clinic staff and/or subjects who have a financial interest in the study or who have an immediate family member of either the clinic staff and/or Indivior employees directly involved in the study.
-

5.4 Subject Screening

Subjects who provide written informed consent will enter a Screening Period to confirm study eligibility.

Eligible subjects will be advised to abstain from short-acting opioids (such as morphine sulfate, oxycodone, hydromorphone, oxymorphone or codeine) for at least 6 hours and long-acting opioids (such as methadone or levorphanol) for 24 hours before arriving at the clinic on the morning of Day 1. Eligible subjects will be informed that under-reporting of the last use of opioids puts him/her at higher risk for rapid and intense onset of withdrawal symptoms. Eligible subjects will also be advised to abstain from alcohol before checking into the clinic.

5.5 Day 1 Check-in Criteria

Subjects must meet all of the following criteria to check into the clinic:

1. All childbearing female subjects must have a negative urine pregnancy test.
2. Subject self-reports/TLFB that they have not had any long-acting opioids within 24 hours.
3. Blood alcohol concentration (per breathalyser) is not of concern to the Investigator.
4. Subject is not taking any medications (illicit or prescribed) contraindicated for use with buprenorphine as per local prescribing information, including benzodiazepines or any other central nervous system (CNS) depressants.

Subjects who indicate that they have used long-acting opioids within 24 hours, or who have a blood alcohol concentration (per breathalyser) of concern to the Investigator, will not be permitted to check in and may be re-scheduled for check-in within the Screening Period. Subjects who report having used short-acting opioids within 6 hours may be permitted to check in at the discretion of the Investigator.

5.6 Buprenorphine Dosing Criterion

Subjects must be in withdrawal (COWS ≥ 8) to receive 4-mg TM buprenorphine.

If a subject's COWS is not ≥ 8 , the subject may either be re-scheduled for check-in within the Screening Period or remain in the clinic (at the Investigator's discretion), and the COWS may be repeated until the subject achieves a score ≥ 8 . Only when the COWS is ≥ 8 and all pre-buprenorphine assessments have been completed may the subject receive TM buprenorphine.

5.7 SUBLOCADE Dosing Criteria

One hour after TM buprenorphine, the subject will complete pre-dose/SUBLOCADE assessments including COWS, OC-VAS, Sedation VAS, AEs, vital signs and concomitant medications.

Subjects must meet all of the following criteria to receive SUBLOCADE:

1. Subject does not display any allergic/hypersensitivity reaction to buprenorphine.
2. Precipitated withdrawal did not occur from the most recent TM buprenorphine administration.
3. Subject does not display clinical signs of sedation, in the opinion of the Investigator.

5.8 Deviation from Inclusion/Exclusion Criteria

Waivers from inclusion and exclusion criteria are not allowed because they have the potential to jeopardise subject safety, the scientific integrity of the study or regulatory acceptability of the data. Indivior does not grant waivers to the protocol-defined inclusion and exclusion criteria, and strict adherence to these criteria as outlined in the protocol is essential.

6 STUDY CONDUCT

6.1 Subject Screening

Study screening begins once written informed consent is obtained; a subject identification number is then assigned. The subject identification number will be used to identify the subject during the screening process and throughout study participation, if applicable.

The Investigator is responsible for maintaining a master list (i.e., a subject identification list) of all consented subjects and will document all subjects that do not meet study eligibility criteria (i.e., screen failures), including reason(s) for ineligibility (i.e., a subject screening and enrolment log). This document will be reviewed by Indivior or designated representative for accuracy and completeness. Ineligible subjects, as defined by the protocol-specific inclusion and exclusion criteria, should not receive study drug and should be documented as screen failures.

6.2 Screen Failure

A subject will be considered a screen failure if written informed consent is obtained but the subject does not receive TM buprenorphine. Subjects who discontinue from the study before TM buprenorphine administration will not be required to complete an ET or EOT visit. Reasons for screen failure (e.g., withdrawal of consent, does/not meet specified inclusion or exclusion criteria, or does not meet specific Day 1 check-in criteria) will be recorded in the electronic case report form (eCRF).

6.3 Enrolment

A subject will be considered enrolled if he/she receives at least 1 dose of TM buprenorphine.

6.4 TM Buprenorphine Treatment and Early Termination

When an eligible subject's COWS is ≥ 8 and all pre-buprenorphine assessments have been completed, the subject will receive TM buprenorphine. Subjects experiencing precipitated withdrawal will be treated for withdrawal symptoms. If precipitated withdrawal occurs before SUBLOCADE administration, the TM induction may be restarted later on the same day at the discretion of the Investigator, based on the half-life of the opioid reported on the TLFB. Alternatively, the Investigator may permit the subject to return to the facility on another day (within the Screening Period). Returning subjects will repeat all Day 1 scheduled assessments.

A subject will be considered a TM Buprenorphine Early Termination if he/she is dosed with TM buprenorphine but is not dosed with SUBLOCADE. Reasons for early termination (e.g., withdrawal of consent, AE of precipitated withdrawal, allergic/hypersensitivity to buprenorphine) will be recorded in the eCRF. Subjects who discontinue from the study after TM buprenorphine administration and before SUBLOCADE administration, will be withdrawn from the study and contacted via

telephone 24 to 72 hours after TM buprenorphine administration to assess ongoing AEs and concomitant medications only.

6.5 SUBLOCADE Treatment

SUBLOCADE treatment begins when the SUBLOCADE injection is given and ends on Day 29 after all assessments have been made at Visit 6.

6.6 Subject Completion

A completed subject is one that has completed all scheduled visits up to and including the EOT Visit (Day 29).

6.7 Withdrawal and Stopping Criteria

6.7.1 Subject Withdrawal from the Study

If the subject has permanently discontinued study treatment (including depot removal) and is no longer being followed for study assessments and procedures (including follow-up procedures), he/she will be considered withdrawn from the study. The primary reason for withdrawing from the study must be entered into the eCRF (e.g., subject is lost to follow-up, Investigator terminates the study or Investigator's discretion).

Subjects who discontinue from the study before TM buprenorphine administration will be considered a screen failure and will not be required to complete an ET or EOT visit.

Subjects who discontinue from the study after TM buprenorphine administration, and before SUBLOCADE administration will not be required to complete an EOT visit but will be contacted via telephone 24 to 72 hours after TM buprenorphine administration to assess AEs and concomitant medications only.

All subjects who receive SUBLOCADE (including those who wish to discontinue early), will be encouraged to attend the EOT visit 28 days after SUBLOCADE administration (Day 29), as well as the EOS visit via telephone (Day 43).

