1. Upon arriving at the clinic, subjects will provide a urine sample for a UDS for qualitative and quantitative analysis, a urine sample for a pregnancy test (child-bearing females only), perform an alcohol breathalyser test and self-report their concomitant medications since screening and recent illicit drug use (including the use of a TimeLine Follow Back [TLFB]). If subject is deemed eligible for check-in the subject will then be assessed for withdrawal symptoms using COWS and for craving using OC-VAS.
 2. Details subjects illicit drug use, in addition to report question capturing frequency, route and date of last use.
 3. Required for female subjects of childbearing potential only.
 4. Per Investigator's discretion, subjects with positive test may either remain in the clinic or be re-scheduled to return on another date.
 5. Per Investigator's discretion, subjects with COWS <8 may either remain in the clinic and repeat assessments at a later time or be re-scheduled to return on another date. The COWS may be repeated at any time, per Investigator's discretion, and should always be repeated just before TM-BUP and SUBLOCADE administration. The OC-VAS should be performed each time a COWS assessment is performed.
 6. If the subject is asleep at 16 and 20 hours, the assessments will not be performed, and the reason should be noted in the CRF.
 7. Includes a review of any previous (taken since screening) and ongoing medications (including over-the-counter) and herbal supplements.
 8. Includes systolic and diastolic blood pressure, pulse rate, respiratory rate and oral temperature after the subject has been in a sitting position for ≥ 3 minutes.
 9. An ECG will be collected after the subject has been in a supine position for ≥ 5 minutes.
 10. Eligible subjects must meet the buprenorphine dosing criterion, prior to receiving 4mg TM buprenorphine.
 11. A sub-set of serum chemistry to be performed including: ALP, ALT, AST, bilirubin, albumin, total protein, GGT and LD only. For increased LFTs, subject should be asked to return to the clinic for weekly repeat liver chemistry testing (ALP, ALT, AST, and total bilirubin) until resolved, stabilised or return to within baseline values, per Section 8.2.7.3.
 12. Weight to be captured; BMI will be calculated in the database using height from screening.
 13. Assessment to be performed anytime pre-SUBLOCADE dose.
 14. Eligible subjects meet SUBLOCADE dosing criteria, prior to receiving SUBLOCADE.

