14.2 Sample Size

Approximately 15 adult subjects with moderate to severe OUD are planned to be dosed with SUBLOCADE. If a subject prematurely discontinues from the study, additional subjects may be enrolled to ensure that 15 subjects are dosed with SUBLOCADE and are evaluable for precipitated withdrawal (see Section 14.3.1).

With a sample size of 15, the probability to observe at least one case of precipitated withdrawal is 79.4%, assuming the true event rate is 10%, while the probability to observe at least one case of precipitated withdrawal is reduced to 53.7% if the true event rate is 5%. Table 4 provides the probabilities of observed events at different true event rates.

Table 4 Probabilities of Observed Events at Different True Event Rates

| True Event Rate | 0 event | At Least 1 Event | At Least 2 Events | At Least 3 Events |
|-----------------|---------|------------------|-------------------|-------------------|
| 1% | 0.860 | 0.140 | 0.010 | 0.0004 |
| 5% | 0.463 | 0.537 | 0.171 | 0.036 |
| 8% | 0.286 | 0.714 | 0.340 | 0.113 |
| 10% | 0.206 | 0.794 | 0.451 | 0.184 |
| 15% | 0.087 | 0.913 | 0.681 | 0.396 |
| 20% | 0.035 | 0.965 | 0.832 | 0.602 |

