1.1 Version History

Table 1 SAP Version History Summary					
SAP Version	SAP Approval Date	Associated Protocol	Protocol Amendment Approval Date	Change	Rationale
1.0	09Sep2019	Amendment 1	14Aug2019	Not Applicable	Original version
2.0	19Dec2019	Amendment 1	14Aug2019	Described the COWS total score increase of ≥ 6 key endpoint in terms of the cumulative event rate.	To align with updated main analytical approach as Kaplan-Meier.
				Defined the evaluable subjects as having COWS assessments for the key timepoints.	To align with updated main analytical approach of survival analysis.
				Clarified definition of Full Analysis Set.	To align with updated main analytical approach of survival analysis.
				Clarified definition of PK Analysis Set.	To state number of concentration samples required for inclusion.
				Clarified definitions of baseline.	Clarification.

SAP Version	SAP Approval Date	Associated Protocol	Protocol Amendment Approval Date	Change	Rationale
				Defined analysis phases.	To clarify analysis with respect to different study phases.
				Changed description of disposition summary.	To align with analysis phases.
				Added summary of entry criteria failed.	To facilitate reporting by supplementing the listing of failed entry criteria.
				Changed main analytical approach for COWS total score increase of ≥ 6 to Kaplan-Meier using key timepoints. Added stratification sensitivity analysis for number of TM BUP doses post-SUBLOCADE and enrolment before/after re-training.	To account for missing COWS assessments in the first 48 hours post-SUBLOCADE, which was unexpected. Evaluate impact of stratification variables on response.
				Added a sensitivity analysis of COWS total	In consideration of potential for informative missing COWS

SAP Version	SAP Approval Date	Associated Protocol	Protocol Amendment Approval Date	Change	Rationale
				score increase of ≥ 6 utilizing event adjudication.	assessments in the first 48 hours post-SUBLOCADE.
				Corrected the equation for COWS AUC and clarified details of the calculation, including times used and normalization.	Correction and clarification.
				Clarified analysis of change from baseline COWS total scores and OC-VAS scores.	To align with clarification of baseline definitions.
				Clarified definition of precipitated withdrawal following induction dose of TM BUP.	To align with clarification of baseline definitions.
				Clarified calculation of AUC_{inf} for NMP	Clarification.

Table 1 SAP Version History Summary					

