2 STATISTICAL HYPOTHESES

For this single arm study, the analysis methods are estimation (for cumulative event rate of COWS increase ≥ 6 within the first 1, 6, 12, 24, and 48 hours) and description (COWS AUC within the first 1, 6, 12, 24, and 48 hours, and COWS and OC-VAS absolute scores and change from pre-treatment values at each timepoint). Therefore, statistical testing and hypotheses are not applicable.

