5.3.2 COWS Total Score Increase by ≥ 6 - Main Analytical Approach

The cumulative event rate for COWS Total Score increase by ≥ 6 from the pre-SUBLOCADE value will be estimated via the Kaplan-Meier method (1958), using the 5 key timepoints, 1, 6, 12, 24 and 48 hours after SUBLOCADE administration (i.e., time=0). Note that for the 1-hour key timepoint the event is referred to as precipitated withdrawal. A subject will be considered in the risk evaluation set at a specific key timepoint if the subject had a pre-SUBLOCADE COWS assessment and either 1) an increase in COWS by ≥ 6 from the pre-SUBLOCADE value within the current time interval (from the previous key timepoint to the current key timepoint), or 2) had a COWS assessment at the current key timepoint and all the prior key timepoints. If a subject has missing COWS assessment at one or more above key timepoints (1, 6, 12, 24 and 48 hours after SUBLOCADE administration), the subject is censored at the last key timepoint prior to the first missing timepoint.

The values for the event occurrence, time, and censoring parameters are assigned sequentially for the subject disposition events according to the order and criteria in Table 7.

Table 7 Parameters for Kaplan-Meier Method

Order of assignment	Disposition Event	Event of COWS Total Score Increase by ≥ 6	Time (hours)	Censored
1	An increase in COWS total score by ≥ 6 from the pre-SUBLOCADE value at any timepoint (scheduled or unscheduled) within 48 hours after SUBLOCADE injection	Yes	Nominal time of the first key timepoint on or after the COWS assessment meeting an increase in COWS total score by ≥ 6 from the pre-SUBLOCADE value	No
2	Missing COWS assessment at a key timepoint and without an increase in COWS total score by ≥ 6 from the pre-SUBLOCADE value within 48 hours	No	Nominal time of last key timepoint prior to the first missing key timepoint (i.e., 0, 1, 6, 12 or 24)	Yes
3	Completed COWS assessment at 1, 6, 12, 24, and 48 hours and without an increase in COWS total score by ≥ 6 from the pre-SUBLOCADE value within 48 hours	No	48	Yes

A Kaplan-Meier plot of the cumulative event rate from time=0 to 48 hours will be produced.

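### No COWS is required when an injected subject leaves before 48 h, so if unscored withdrawal prompts the departure, the main cumulative event rates are biased low

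*Protocol*

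**What the plan says.** **Leaving after the injection**
- Protocol 6.7.1: "All subjects who receive SUBLOCADE (including those who wish to discontinue early), will be encouraged to attend the EOT visit 28 days after SUBLOCADE" administration. The same sentence extends the encouragement to the Day 43 telephone contact. No rating is tied to the moment of leaving.
- Protocol 6.4 and Table 1 note 18 define an early-termination contact, but only for subjects given TM buprenorphine and not SUBLOCADE.
- Protocol Table 2 footnote 5: "The COWS may be repeated at any time", at the investigator's discretion. A repeat is mandatory only just before each of the two drugs is given. Footnote 18 ties check-out to having finished the scheduled assessments and is silent on leaving sooner. Under 6.7.2, tests after withdrawal of consent are optional.

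**Analysis**
- SAP 5.3.2: if a key timepoint (1, 6, 12, 24 or 48 h) has no score, "the subject is censored at the last key timepoint prior to the first missing timepoint". Table 7 row 2 sets the event to No. Row 1 is applied first and counts a rise of 6 or more at any rating up to 48 h, including unscheduled ones.
- SAP 1.1 gives the reason for the adjudication sensitivity analysis: "In consideration of potential for informative missing COWS" assessments in the first 48 h. SAP 6.2 says Kaplan-Meier became the main method because of the extent of missing COWS.

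**Size and aim**
- Protocol 14.2: "Approximately 15 adult subjects with moderate to severe OUD are planned to be dosed with SUBLOCADE". On replacement: "If a subject prematurely discontinues from the study, additional subjects may be enrolled".
- SAP 2: the aim is estimation, and "statistical testing and hypotheses are not applicable".

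**The concern.** Kaplan-Meier treats a censored subject as having the same future risk as those still under observation. Here that assumption is doubtful for one kind of missing score. Protocol 1.3.1 names a prolonged withdrawal state as a specific risk of the injection, and a subject in worsening withdrawal may well walk out. The worst score may then never be taken, and the analysis treats the departure as unrelated to the event being counted. Any resulting error favours the regimen, and in a study of 15 subjects one missed event moves the estimate visibly. The adjudicators can judge from other records that withdrawal occurred, but they cannot supply a score that nobody took.

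**Working it through.** **1. The plan's own figure.** The chance of at least one event among 15 is 1 − (1 − p)^15. At p = 10%: 1 − 0.90^15 = 0.794. At p = 5%: 1 − 0.95^15 = 0.537. Both match Protocol 14.2. All cells of Protocol Table 4 agree to within 0.001; the largest difference is at 20% and at least 2 events (0.833 computed, 0.832 printed).

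**2. How long a subject can go unrated.** SAP Table 4 schedules COWS at 1, 2, 3, 4, 6, 8, 12, 16, 20, 24, 30, 36 and 48 h. The gaps from injection are 1, 1, 1, 1, 2, 2, 4, 4, 4, 4, 6, 6 and 12 h. The longest is 12 h, from 36 to 48 h. The stretch from 12 to 24 h also becomes 12 h if the subject is asleep at both 16 and 20 h (Protocol Table 2 footnote 6).

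**3. Where a leaver is censored.** Only the five key timepoints set the censoring time. A subject who leaves just before 48 h, with scores at 24, 30 and 36 h and no rise of 6, is censored at 24 h.

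**4. Effect on the 48 h rate.** Assumption: k subjects leave between 6 and 12 h with an unscored rise of 6 or more. Under Table 7 row 2 they are censored at 6 h. Had a departure COWS been taken, row 1 would place their event at 12 h. The estimate is 1 − Π(1 − d/r) over the key timepoints, where d is the number of events and r the number at risk.

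No other events, N = 15:
- SAP: d = 0 throughout, so 0% for any k.
- Scored: at 12 h, d = k and r = 15, so k/15.

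| k | N | Other scored events | SAP 48 h rate | If leavers were scored | Difference (points) |
|---|---|---|---|---|---|
| 1 | 15 | none | 0% | 1/15 = 6.7% | 6.7 |
| 2 | 15 | none | 0% | 2/15 = 13.3% | 13.3 |
| 1 | 15 | one at 1 h | 1/15 = 6.7% | 2/15 = 13.3% | 6.7 |
| 2 | 15 | one at 1 h | 1/15 = 6.7% | 3/15 = 20.0% | 13.3 |
| 1 | 15 | one at 24 h | 1/14 = 7.1% | 2/15 = 13.3% | 6.2 |
| 2 | 15 | one at 24 h | 1/13 = 7.7% | 3/15 = 20.0% | 12.3 |
| 1, replaced | 16 | none | 0% | 1/16 = 6.3% | 6.3 |
| 2, replaced | 17 | none | 0% | 2/17 = 11.8% | 11.8 |

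Clopper-Pearson 95% intervals (the method named in Protocol 14.4.1) are 0 to 21.8% for 0/15, 0.2 to 31.9% for 1/15 and 1.7 to 40.5% for 2/15.

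**5. Effect on the stated detection probability.** If a share m of true events goes unscored, the effective rate is p(1 − m). At p = 10%, m = 25% gives 1 − 0.925^15 = 0.689, and m = 50% gives 1 − 0.95^15 = 0.537, against the planned 0.794. The values of m are assumptions.

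**The case against.** The strongest reply is that the plan already catches most of this. Ratings are 1 to 4 h apart over the first 24 h for a subject who is awake. Footnote 5 allows a repeat whenever the investigator wants one, and Protocol 8 allows any assessment more often if clinically indicated. A rise of 6 or more at any rating overrides censoring. Subjects who leave the clinic but stay in the study still have weekly COWS visits, and a missed visit must be followed up (6.7.3). The main reason for withdrawing from the study is already recorded. External adjudicators review the first 48 h, and SAP 5.5.2 plans a chronological listing of COWS with AEs.

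Most of that stands, and it rules out several stronger readings that a reader might infer:
- That withdrawal driving someone out necessarily goes unscored. It may, but a scheduled or discretionary rating may have caught it.
- That a leaver is carried to 48 h as event-free. The subject leaves the risk set; in the 24 h example above, the SAP rate is 7.1%, not 6.7%.
- That each missed event costs 6.7 points. That depends on when other events fall and whether leavers are replaced.
- That subjects did leave early. SAP 1.1 and 6.2 report missing COWS but give no cause.
- That Day 29 and Day 43 are the only later contacts. They are not for those who stay in the study, although no later visit can supply a score inside 48 h.

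What the reply does not remove is that a departure score is permitted but not required, and that without it the main analysis assumes departure is uninformative.

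**Conclusion.** The gap is real and the bias is conditional. It needs two things: withdrawal prompts the departure, and no rise of 6 or more was scored beforehand. If both hold, the main 6 to 48 h cumulative rates are too low. The adjudication analysis is then the only planned route to recover the event, and it rests on clinical judgement. For one or two such leavers among 15, the illustrative shortfall at 48 h is about 6 to 7 or 12 to 13 percentage points. The number of leavers and their time of leaving are assumptions; the documents give neither. With intervals as wide as 0.2 to 31.9%, the study remains imprecise either way, so this is a worthwhile low-cost improvement and not a fatal flaw.

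**What to change.** **Protocol 6.7.1 and a Table 2 footnote.** Require that a COWS, with OC-VAS and AE review, be attempted for any injected subject leaving before the 48 h assessment. Record it as unscheduled, with the actual time, the reason for leaving and any refusal. For subjects in the FAS, Table 7 row 1 already counts such a score, so the main analysis needs no new rule.

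**SAP 5.3.3.** Add a sensitivity analysis that counts as events those who leave before 48 h without a departure COWS. This bounds the bias from refusals, and it is the only remedy for anyone who has already left. State how it treats a subject who leaves before any scheduled post-injection COWS. The SAP's FAS definition excludes that subject even if an unscheduled departure score exists.

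**Cost.** One sentence, one footnote and one extra analysis, plus a short rating by staff already on site, for early leavers only. Some will decline. The bound will look less favourable than the main estimate, and a rise that begins after departure will still be missed.
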